To assess the safety and tolerability in subjects treated with OCA compared to placebo.

Methodology:

This Phase 3b, double-blind, randomized, placebo-controlled, multicenter study will evaluate the effect of OCA on clinical outcomes in subjects with PBC. Subjects will be screened twice during a 1 to 8-week Screening period prior to entering the study to allow for the collection of repeat serum chemistry samples (at least 2 weeks apart) to confirm pretreatment alkaline phosphatase (ALP) and total bilirubin values (refer to [Section 9.7.6](#)).

Investigational product will be taken orally, once daily for the majority of subjects; dose and frequency will be modified for subjects with cirrhosis (including subjects progressing to cirrhosis during the study) and classified as Child-Pugh B or C. The randomization will be stratified by ursodeoxycholic acid (UDCA) treatment (yes/no) and baseline bilirubin categories ($>$ upper limit of normal [ULN]/ \leq ULN).

Schematic Diagram:

EOS = end of study; ULN = upper limit of normal

Initial dose titration of investigational product should occur at the Month 3 visit, or any study visit thereafter for subjects on all dosing regimens, based on tolerability. Subsequent dose titration(s) for subjects classified as Child-Pugh B or Child-Pugh C and following a modified dosing schedule may occur no earlier than 6 weeks after the previous dose titration.

Dosing frequency will be determined by the presence or absence of cirrhosis and, if cirrhosis is present, by Child-Pugh Score as described below:

- Non-cirrhotic subjects or subjects classified as Child-Pugh A at screening will receive 5-mg OCA or matching placebo once daily for 3 months. Subjects should titrate to a

maximum dose of 10-mg OCA once daily (or matching placebo) at the Month 3 visit or at any study visit following the Month 3 visit based on tolerability of the product.

- For those subjects that up-titrate to 10 mg, dosing may be decreased to 5 mg at any time during the study as considered clinically appropriate (eg, based on tolerability). Subjects may be titrated back to a maximum dose of 10 mg once daily based on tolerability and clinical judgment of the Investigator.

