7.4. Dose Titration Criteria

Dose titration may follow the scheduled dosing regimens described in [Section 7.3](#) or occur due to tolerability concerns or as a result of changes in a subject's cirrhosis status (using histology or non-histological methods as defined in [Section 9.7.3](#) and [Section 9.7.4](#)) or Child-Pugh Score.

Scheduled Dose Titration - The first dose titration for any subject may occur no earlier than 3 months following initiation of OCA or matching placebo. Subsequent titrations in dose or dosing frequency for subjects following the Modified Dosing Regimens may occur no earlier than 6 weeks (via an unscheduled visit or regular visit- see [Appendix A](#)) following an up-titration.

Tolerability Dose Titration - Investigators may decrease the dosing frequency or dose for any subject at any time during the study, as considered clinically appropriate (eg, tolerability; see [Section 7.4.2](#)).

Dose Titration due to Change in Cirrhosis or Child-Pugh Score - When subjects demonstrate a change in cirrhosis status (as assessed per [Section 9.7.3](#)) or Child-Pugh Score ([Section 9.7.4](#)), dosing should be reassessed and the dosing regimen modified appropriately. Changes to the dosing regimen are not mandatory and should be based on clinical judgment as well as change in cirrhosis status. [Table 5](#) provides an overview of the possible changes in dosing regimen due to changes in cirrhosis or Child-Pugh Score. Dosing should follow the titration schedule of the new dosing regimen such that the maximum dose within that dosing regimen is ultimately attained, based on tolerability and clinical judgment.

Table 5: Changes in Dosing Regimen Due to Changes in Cirrhosis Status or Child-Pugh Score

Original Status	New Status ^a		
	Non-cirrhotic OR Child-Pugh A	Child-Pugh B	Child-Pugh C
Non-cirrhotic or Child-Pugh A	No Change	10 mg daily → 5 mg daily 5 mg daily → No change or 10 mg twice weekly ^b	5 mg or 10 mg daily → 10 mg twice weekly ^b
Child-Pugh B	5 mg daily → 10 mg daily	No Change	5 mg daily → 10 mg twice weekly ^b 10 mg twice weekly ^b → No change or 5 mg twice weekly 5 mg twice weekly ^b → No change or 5 mg once weekly
Child-Pugh C	10 mg twice weekly → 5 mg daily	10 mg twice weekly → 5 mg daily 5 mg twice weekly → No change or 10 mg twice weekly ^b 5 mg once weekly → 5 mg twice weekly	No Change

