^a Once a subject begins dosing with the new dosing regimen, titration should occur as described for that dosing regimen in [Section 7.3](#) or [Appendix A](#).

^b Dosing per the twice weekly schedule must be at least 3 days apart.

Subjects who exhibit development of cirrhosis at any point in the study should be assessed per [Section 9.7.3](#). If the presence of cirrhosis is confirmed and the subject's Child-Pugh score is either B or C, the appropriate modified dosing regimen should be followed. The dose or frequency of investigational product should be down-titrated to the next lowest dosing frequency in the appropriate modified dosing regimen unless the subject is currently taking a dose and frequency also specified in the modified dosing regimen and the Investigator determines that it is clinically appropriate for the subject to continue at that dose (Appendix A).

Subjects with pre-existing cirrhosis who demonstrate a change in the Child-Pugh Score from A to B or C at any point in the study should also have their dosing modified per the appropriate dosing regimen (Appendix A).

Subjects who demonstrate an improvement in cirrhosis status or in Child-Pugh Score from B to A, or from Child-Pugh C to B, may be eligible to transition to the standard dosing regimen or the modified dosing for Child-Pugh B, respectively, based on tolerability. Prior to any dosing change, subjects must meet pre-titration assessment requirements for dosing as described in [Section 7.4.1](#).

Child-Pugh Scores will be calculated at all quarterly study visits. All associated visit data (including central laboratory results) should be entered into the eCRF in a timely fashion to confirm that the subject's Child Pugh Score has not changed. If a change in cirrhosis status (as defined in [Section 9.7.3](#)) and/or Child-Pugh Score is observed independent of a study visit, the subject should be contacted via phone to discuss the need for a dosing modification and should be asked to return to the investigative site as soon as possible if a new bottle of investigational product is required to be dispensed.

Subjects' dose and dosing frequency may be titrated up or down within the appropriate dosing regimen based on the calculated Child-Pugh Scores. Up-titration should be done per Investigator discretion and be guided by the pre-titration tolerability assessments.

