9.7.3. Assessing Cirrhosis

To determine which dosing regimen subjects should follow, the presence or absence of cirrhosis should be assessed by the Investigator at Screening Visit 1. Acceptable methods of confirming (via medical history) or assessing cirrhosis for purposes of the study is defined as a subject who has documented evidence or presence of one or more of the following cirrhosis indicators:

- Biopsy results consistent with PBC Stage 4 ([Ludwig 1978](#))
- Transient Elastography Median Value ≥ 16.9 kPa ([Corpechot 2012](#))
- The presence of any of the following (unless exclusionary per [Section 8.3](#)) in the absence of acute liver failure:
 - Varices
 - Ascites
 - Radiological evidence of cirrhosis (nodular liver or enlargement of portal vein and splenomegaly)
- Combined low platelet count ($<140\,000/\text{mm}^3$) with:
 - persistent decrease in serum albumin, or
 - elevation in prothrombin time /INR (not due to antithrombotic agent use), or
 - elevated bilirubin ($2\times$ ULN)

Subjects who exhibit no evidence of cirrhosis by the above methods of assessment will be dosed using the Standard Dosing Regimen, while those who do exhibit evidence of cirrhosis by one or more of the above methods will be dosed using the Modified Dosing Regimen according to their Child-Pugh Score calculated in the electronic case report form (eCRF) (see [Appendix A, Section 7.3, Table 3 and Table 4](#)).

Cirrhosis status should be reassessed as clinically indicated throughout the study. Any change in cirrhosis status will necessitate re-evaluation of the dosing regimen.

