following review of the pre-titration laboratory results to assess safety and tolerability, the dosing frequency of 5 mg OCA or matching placebo should be increased to twice weekly (at least 3 days apart). Subjects who have maintained the twice weekly dosing frequency for a minimum of at least 6 weeks, and meet the dose titration criteria, should up-titrate to twice weekly dosing with 10 mg OCA or matching placebo. Subjects with at least 6 weeks of twice weekly dosing at 10 mg OCA or matching placebo, and meeting dose titration criteria, should up-titrate to the maximum allowed dose of 5 mg OCA or matching placebo once daily.

Investigators may decrease the dosing frequency (back to once or twice weekly) or dose for any subject at any time during the study, as considered clinically appropriate (eg, tolerability).

Modified Dosing Regimen for Subjects with Child-Pugh C Hepatic Impairment

Subjects with cirrhosis and classified as Child-Pugh C at Screening will follow a modified dosing schedule receiving 5 mg OCA or matching placebo once weekly as described in [Figure 2](#). After a minimum of 3 months dosing once weekly with 5 mg OCA or matching placebo, and following review of the pre-titration laboratory results to assess safety and tolerability, the dosing frequency of 5 mg OCA or matching placebo should be increased to twice weekly (at least three days apart). Subjects who have maintained the twice weekly dosing frequency for a minimum of at least 6 weeks, and meet the dose titration criteria, should up-titrate to the maximum allowed dose of 10 mg OCA or matching placebo twice weekly.

Investigators may decrease the dosing frequency (back to once weekly) or dose for any subject at any time during the study, as considered clinically appropriate (eg, tolerability).

Dose Titration due to Change in Cirrhosis or Child-Pugh Score

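### Section 7.4 leaves dose reduction on reaching Child-Pugh B or C optional, against the synopsis, so 10 mg daily may continue at twice the Child-Pugh B maximum

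*Protocol*

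**What the plan says.** The dosing rules for a subject whose liver disease worsens on study stand in several places in the current protocol text.

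- **Synopsis, Methodology.** Once-daily dosing applies to most subjects, but "dose and frequency will be modified for subjects with cirrhosis (including subjects progressing to cirrhosis during the study") who are in Child-Pugh B or C. The wording is unconditional.
- **Section 7.4, paragraph on change in cirrhosis or Child-Pugh Score.** Dosing should be reassessed and the regimen adapted, and then: "Changes to the dosing regimen are not mandatory and should be based on clinical judgment as well as change in cirrhosis status".
- **Section 7.4, text after Table 5.** With confirmed cirrhosis and Child-Pugh B or C, the dose or frequency "should be down-titrated to the next lowest dosing frequency in the appropriate modified dosing regimen unless the subject is currently taking a dose" and frequency that the modified regimen also contains and the Investigator finds it appropriate to continue. Subjects with existing cirrhosis who move from A to B or C "should also have their dosing modified per the appropriate dosing regimen".
- **Appendix A, paragraph on change in cirrhosis or Child-Pugh Score.** It repeats the not-mandatory clause. It opens with subjects already on a modified regimen, but its list of scenarios includes new cirrhosis in class B or C and moves from A to B or C.
- **Appendix A, regimens by class.** Class B subjects "should up-titrate to the maximum allowed dose of 5 mg OCA or matching placebo once daily"; class C subjects "should up-titrate to the maximum allowed dose of 10 mg OCA or matching placebo twice weekly".

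**The concern.** A site that follows the synopsis must change the dose of a subject who progresses to cirrhosis with Child-Pugh B or C. A site that follows the not-mandatory sentence in Section 7.4 need not. Two sites can therefore treat the same confirmed case differently, one of them above the top dose of the class, and neither breaks a binding instruction.

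This matters because Section 5.5.2.2 concludes that subjects with hepatic impairment should receive somewhat lower doses so that liver exposure stays similar. Leaving 10 mg daily unchanged runs against that rationale. Section 7.1 describes the enrolled subjects as being at higher risk of liver-related complications, so progression to class B or C is foreseeable, although the protocol does not state how many subjects it expects to progress.

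**Working it through.** The protocol gives no figure for this point, so there is none to reproduce. The check has three parts.

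**1. Weekly doses.** The inputs are the regimen maxima in Section 7.3 (Table 3) and Appendix A (Table 11). Weekly dose = tablet strength × doses per week.

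| Regimen | Calculation | mg/week |
|---|---|---|
| Standard maximum, 10 mg daily | 10 × 7 | 70 |
| Class B maximum, 5 mg daily | 5 × 7 | 35 |
| Class C maximum, 10 mg twice weekly | 10 × 2 | 20 |
| 5 mg twice weekly | 5 × 2 | 10 |

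Ratio = weekly dose kept ÷ weekly maximum of the new class.

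- 10 mg daily kept on reaching B: 70/35 = 2.0
- 5 mg daily kept on moving from B to C: 35/20 = 1.75
- 10 mg daily kept in C: 70/20 = 3.5. This needs a direct move from A to C, or a reduction passed over at B and again at C.

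**2. Is there a binding ceiling elsewhere?**

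- Section 7.4.1 is binding, but only on increases: a subject with total bilirubin above twice baseline and above ULN cannot be up-titrated.
- Section 7.4.2 says the dose may be lowered or stopped for tolerability.
- Sections 8.4.1, 8.4.2 and 9.2.1 require stopping for pregnancy, liver transplant and continued commercial OCA. None refers to Child-Pugh class.
- Section 8.4.2.1 calls for repeat testing and follow-up of raised liver tests, with no dose action.

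So there is a hard limit on raising the dose when bilirubin worsens, and none on continuing a dose above the class maximum.

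**3. What Table 5 shows about intent.** Table 5 has seven entries for worsening status.

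| Move | Dose at the time | mg/week against new maximum | No change offered? |
|---|---|---|---|
| A to B | 10 mg daily | 70 > 35 | No |
| A to C | 10 mg daily | 70 > 20 | No |
| A to C | 5 mg daily | 35 > 20 | No |
| B to C | 5 mg daily | 35 > 20 | No |
| A to B | 5 mg daily | 35 = 35 | Yes |
| B to C | 10 mg twice weekly | 20 = 20 | Yes |
| B to C | 5 mg twice weekly | 10 < 20 | Yes |

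Here A includes non-cirrhotic subjects. All four entries above the new maximum give only a reduction, and all three at or below it allow the dose to stay. This matches the exception after Table 5, which protects only a dose already in the modified regimen. The blanket sentence in Section 7.4 removes that distinction. Table 5 is evidence of intent only, since Section 7.4 presents it as an overview of changes that are possible.

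**The case against.** The strongest defence is that specific text governs general text. The passage after Table 5 tells sites to follow the modified regimen and to down-titrate, with one exception that 10 mg daily cannot meet. The not-mandatory sentence covers every direction of change, including improvement and doses already within the class, where discretion is reasonable. Discretion also has a clinical basis: under Table 6, bilirubin above 3.0 mg/dL scores 3 points, and with the other four factors at 1 point each the total is 3 + 4 = 7, which is Grade B. One analyte can therefore change the class of a cirrhotic subject in a trial that selects for raised bilirubin.

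Much of this stands, and it limits the point. It does not remove it: the specific text is a recommendation, the general sentence expressly withdraws any obligation, and the synopsis states an obligation. Appendix A already deals separately with short-lived laboratory changes that have a known cause, so the blanket sentence is not needed for them.

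A reader might infer more than the document supports:

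- **That Section 9.7.3 is contradicted too.** Its statement that cirrhotic subjects "will be dosed using the Modified Dosing Regimen according to their Child-Pugh Score" follows from the assessment at Screening Visit 1. For a change on study it asks only that the regimen be re-evaluated, which fits Section 7.4.
- **That Table 5 is contradicted.** An entry such as "5 mg or 10 mg daily → 10 mg twice weekly" sits in a list of possible changes, so it does not contradict a statement that changes are optional.
- **That Appendix A already sets a ceiling for progressors, or by itself permits 10 mg daily.** Its maximum-dose wording is written for subjects in class B or C at Screening. Its not-mandatory clause opens with subjects on a modified regimen, whose planned maximum is 5 mg daily. The text is loose because its scenarios go wider.
- **That harm is shown.** Section 5.5.2.2 predicts liver exposure, at the stated site of action, rising 1.5-fold (B) and 1.7-fold (C), and reports no apparent effect on overall safety at much higher plasma exposure. Child-Pugh scoring and laboratory tests continue quarterly. Ratios of weekly milligrams do not measure risk.

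**Conclusion.** The conflict between the synopsis and Section 7.4 is real, and Section 7.4 sits badly with its own later text. The consequence is a missing ceiling: in confirmed cirrhosis with Child-Pugh B, 10 mg daily may continue at 2.0 times the class maximum, and 5 mg daily kept on moving from B to C is 1.75 times. The figure of 3.5 is arithmetically right but is an extreme case and should not be taken as typical.

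The ratios assume that dose is compared by weekly milligrams and that cirrhosis is confirmed, since Table 4 keeps non-cirrhotic subjects on the standard regimen whatever their score. The number of subjects affected cannot be derived from the protocol, and no effect on safety or efficacy is claimed. This is an inexpensive improvement that should be made; it does not call the trial's primary comparison into question.

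**What to change.** In Section 7.4 and Appendix A, replace the not-mandatory sentence with a rule to this effect: once cirrhosis with Child-Pugh B or C is confirmed, the dose must not exceed the class maximum (B, 5 mg daily; C, 10 mg twice weekly). The only exception is a documented, short-lived laboratory change with a known cause. Lower doses, and any increase after improvement, stay at the Investigator's judgment.

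In the synopsis, say that for subjects who progress on study the dose will not exceed the class maximum. The present wording is too strong in the other direction, because Table 5 lets a subject on 5 mg daily stay there on reaching class B. The starting regimens for subjects in class B or C at Screening need no change.

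The cost is text in three places and less Investigator discretion: a subject stable on 10 mg daily would have to be reduced even if the Investigator would have kept the dose. Some subjects would return early for a new bottle when a class change is found between visits, as Section 7.4 already foresees. Matching placebo follows the same rule, so blinding is unaffected, and no extra subjects are needed.

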7.4.1. Pre-Titration Tolerability Assessment Requirements

Tolerability of investigational product must be assessed prior to titrating a subject to a higher dose. A review of adverse events and safety laboratory results (eg, chemistry, hematology, and coagulation) obtained within 2 months of the up-titration visit must be performed as part of the investigational product tolerability assessment, prior to any planned up-titration in study medication (eg, Month 3, Month 6). Safety laboratory results obtained at the Month 1 visit (for titration at Month 3) or at the 1 Month Post-Titration Assessment visit (for titration prior to or at the subsequent quarterly visit) are acceptable for review purposes; however, if for any reason, laboratory results are not available at the time of the planned up-titration visit, additional laboratory samples must be obtained and reviewed, prior to up-titrating the subject to a higher dose.

To be eligible for a dose up-titration:

- Subjects should not be experiencing significant AEs that are suspected to be related to investigational product (eg, severe pruritus) or displaying other symptoms that may indicate intolerability of investigational product.
- There must be no clinically significant increase (as determined by the investigator) in the subject's liver function tests. Subjects whose total bilirubin is $>2\times$ baseline (and $>ULN$) cannot be up-titrated, and additional unscheduled safety visit procedures, outlined in [Section 9.7.19](#), should be implemented, as required.

7.4.2. Safety Criteria for Adjustment or Stopping Doses

Investigational product may be temporarily decreased (eg, from 10 mg to 5 mg daily, or by decreasing dosing frequency) or temporarily or permanently stopped based on tolerability concerns. The dose of investigational product should be resumed to the maintenance dose in a blinded manner once the issues relating to the lack of tolerability are resolved.

Subjects that discontinue investigational product are expected to continue in the study (and follow the regular visit schedule) until the end of the study, and the study will only terminate at the time when the needed number of adjudicated events has accrued. If a subject reaches an event, he or she should continue the regular visit schedule and continue taking investigational product as long as the Investigator assesses it as safe. In general, subjects should be strongly encouraged to both stay on investigational product and remain in the study until study termination.

7.5. Criteria for Study Termination

The Sponsor reserves the right to terminate the study at any time. It is normal procedure to review the emerging clinical and safety data. As a result of such a review or a recommendation by the DMC, it may be necessary to stop the study before all events have been accrued, and when subjects are still active on the study. In addition, the Sponsor may terminate the study at

an investigational site at any time (eg, poorly performing sites, as determined by the number of subjects enrolled or the quality of the study data).

The Investigator and/or Sponsor (or designee) must notify the Institutional Review Board/Independent Ethics Committee (IRB/IEC) of discontinuation of a site or the study and the reason for doing so.

Investigators will be informed by the Sponsor as to when the final study visit is to be completed, and should then schedule all subjects for the End of Study Visit. The window of time for scheduling the visit will be based on a final projection of when the requisite 121 adjudicated events will have been accrued.

8. SELECTION AND WITHDRAWAL OF SUBJECTS

8.1. Subject Population

This study will be conducted at approximately 170 international study sites with experience in treating patients with PBC. Prospective subjects will be identified primarily from the hospital and/or physician's database of patients with PBC, or may be referred from other physicians. Patients may self-refer to an Investigator if they become aware of the study through local, national, or international PBC patient societies, forums, or networks.

